4. ANALYSIS POPULATIONS

All subjects who receive at least 1 dose of ataluren will be included in the analyses of safety. The results from this study will be presented using 4 populations:

Enrolled Subjects: All subjects who were successfully screened and enrolled into the study.

Safety Population: All subjects who receive at least 1 dose of ataluren. The safety population will be used for the safety summary.

PK Population: All subjects who receive at least 1 dose of ataluren and have at least 1 PK concentration data. The PK population will be used for PK analyses.

Evaluable Population: All subjects who receive at least 1 dose of ataluren and have baseline and at least 1 post-baseline measurement for TFTs, NSAA, or response to the *palatability of ataluren* questions. The evaluable population will be used for the efficacy analyses.

5. ANALYSIS CONVENTIONS

Post-text tables and listings will be prepared in accordance with the current ICH Guidelines. The information and explanatory notes to be provided in the footer of each table and listing will include the following information:

1. Date and time of output generation;
2. SAS® program name, including the path that generates the output;
3. Any other output specific details that require further elaboration.

In general, tables will be formatted with a column displaying findings for all subjects combined. Row entries in tables are made only if data exist for at least 1 subject (*i.e.*, a row with all zeros will not appear). The only exception to this rule applies to tables that list the termination status of subjects (*e.g.*, reasons for not completing the study). In this case, zeros will appear for study termination reasons that no subject satisfied. The summary tables will clearly indicate the number of subjects to which the data apply and data points that are “unknown” or “not performed” will be distinguished from missing data.

Individual Subject Data Listings will be sorted and presented by subject number and visit date, if applicable. Listings will also include the number of days relative to the exposure to the study drug (active or placebo), if applicable.

Specific algorithms are discussed for imputing missing or partially missing dates, if deemed appropriate, under specific data topics. Imputed or derived data are flagged in the individual subject data listings. Imputed data will not be incorporated into any raw or primary datasets. The imputed data will be retained in the derived / analysis datasets.

The total duration for a subject *on study* will be calculated as the difference between the date of initial exposure to the study drug and the last day of observation plus one day. All calculations for defining the duration on study will follow the algorithm $DURATION = [STUDY\ COMPLETION\ OR\ WITHDRAW\ DATE - DRUG\ DOSE\ DATE + 1]$.

This section details general conventions to be used for the statistical analyses. The following conventions will be applied to all data presentations and analyses.

- Summary statistics will comprise the number and percentage of responses in each level for categorical variables, and the sample size (n), mean, median, standard deviation (SD), minimum, and maximum values for continuous variables.
- All mean and median values will be formatted to one more decimal place than the measured value. SD values will be formatted to 2 more decimal places than the measured value. Minimum and maximum values will be presented with the same number of decimal places as the measured value.

- The number and percentage of responses will be presented in the form XX (XX.X%).
- Although the primary interest will be descriptive for summarizing the results from this study, there may be interest in calculating probability values for certain parameters for informational purposes. If presented, probability values will be rounded to 4 decimal places. All probability values that round to 0.0000 will be presented as '<0.0001' and p-values that round to 1.0000 will be presented as '>0.9999'. Probability values <0.05 will be considered statistically significant.
- All summary tables will include the analysis population sample size (i.e., number of subjects).
- Study Day 1 is defined as the day the subject is exposed to the study drug. All *study days* are determined relative to the day of exposure to the study drug (active or placebo).
- Baseline values will be defined as those values recorded closest to, but prior to, the first study treatment on Day 1.
- Change from baseline will be calculated as follows:

$$\text{Change} = \text{Post-baseline value} - \text{baseline value}$$

- Missing data may have an impact upon the interpretation of the trial data. However, as this study is of short duration, it is anticipated that missing data will be minimal. Missing data will not be imputed; however, a methodology is defined for missing and partial dates (see Section 9.1.3). In the event of a missing laboratory test result, the result will be treated as missing for the laboratory abnormality summary.
- Date variables will be formatted as DDMMYY for presentation.
- Tables, figures, and listings will be presented in landscape orientation.
- SAS® Version 9.3 or higher will be the statistical software package used for all data analyses.
- The subject number will be included in all data listings. All listings will be sorted by subject number and visit date, as applicable.

6. STUDY DISPOSITION

A complete accounting of subject participation in the study will be presented in Table 14.1.1 entitled *Subject Disposition* (All Screened Subjects). The purpose of this table is to provide an accounting of subjects from their entrance into the study through the final visit and to account for subject evaluation in major analyses of safety and tolerability, including reasons for early study termination. The table will display the number and percentage of subjects that:

- were enrolled,
- are included in the Safety population,
- are included in the PK population,
- are included in the evaluable population
- completed or discontinued the study.

In addition, the reason for early study termination will be summarized separately using the number and percentage of subjects for each reason.

Listing 16.2.1 entitled *Subject Disposition* supports Table 14.1.1. This listing will be sorted by subject number.

Listing 16.2.3.1 entitled *Inclusion and Exclusion Criteria* displays the data from the Inclusion Criteria and Exclusion Criteria case report forms (CRF). The data will be displayed for each subject and for each inclusion criterion not met or each exclusion criterion met. The listing will be sorted by subject number and inclusion/exclusion criterion number.

Listing 16.2.3.2 entitled *Eligibility Criteria* displays the data from the Study Eligibility CRF. This form confirms that the appropriate informed consent has been obtained for study participation. The listing will be sorted by subject number.

7. **PROTOCOL DEVIATIONS**

In accordance with ICH E3, Sponsor-defined eligibility and important post-dosing protocol deviations will be identified and listed separately by subject. Deviation type/code provided by the Sponsor will be used to classify the events as:

- Subjects who developed withdrawal criteria during the study but were not withdrawn
- Subjects who entered the study even though they did not satisfy the entry criteria
- Subjects who received an excluded concomitant treatment
- Subjects who received the wrong treatment or incorrect dose
- Other

Deviations are then categorized into:

- Major
- Minor

Table 14.1.2 entitled *Summary of Protocol Deviations (All Screened Subjects)* will provide a tabular summary of the protocol deviations by category and type of deviation. Listing 16.2.2 entitled *Protocol Deviations* supports Table 14.1.2. The listing will be sorted by subject number and date of the protocol violation.

8. DEMOGRAPHICS AND OTHER BASELINE CHARACTERISTICS

8.1. Baseline Demographic Factors and Medical History

All subjects in the Safety Population will be included in summary of demographic information in Table 14.1.3 entitled *Demographics and Baseline Characteristics* (Safety Population). This table summarizes the subject population with respect to gender, age (years) at screening, race and ethnicity. Age will be reported in months and years and summarized with descriptive statistics: n, arithmetic mean, SD, median, range (*i.e.*, minimum and maximum values). The number and percent of each gender, race, and ethnicity category will be presented using counts and percentages. Race will be presented using the following categories:

- Caucasian or White
- Black or African American
- Asian
- American Indian or Alaska Native
- Native Hawaiian or other Pacific Islander
- Other

The supportive data for Table 14.1.3 are presented in Listing 16.2.4.1 entitled *Demographics and Subject Characteristics* (Safety Population). This listing will be sorted by subject number.

8.2. Medical History

Medical history data will be mapped with the Medical Dictionary for Regulatory Activities (MedDRA) version 19.0 and categorized by system organ class (SOC) and preferred term (PT). The medical history will be summarized using counts and percentages by SOC and PT for the Safety Population in Table 14.1.4 entitled *Summary of Medical History*.

Medical history will be presented in Listing 16.2.4.2 entitled *Medical History (Safety Population)*. This listing will be sorted by subject number and start date of the medical history.

8.3. Prior and Concomitant Medications

A prior medication is a medication that was started and ended prior to the first dose of study medication. Concomitant medications are medications that the subject starts after the first dose of study medication or medications that began prior to the first dose of study medication and continue afterwards.

All prior and concomitant medications will be coded using the Anatomical-Therapeutic-Chemical (ATC) classification text from the WHO Drug Dictionary. Medications will be presented by ATC Class 1, ATC Class 3, and Preferred Term. The data will be presented for subjects in the Safety Population. Subjects will only be counted one time in each unique ATC Class 1, ATC Class 3, and Preferred Term. For the summary tables, the count and percentage of subjects under each anatomical therapeutic chemical (ATC) class and PT will be summarized.

Prior medications will be summarized in Table 14.1.5.1 entitled *Summary of Prior Medications* (Safety Population). Concomitant medications, prescribed and over the counter, that the subject takes or continues to take after the first dose of study medication will be summarized in Table 14.1.5.2 entitled *Summary of Concomitant Medications* (Safety Population). Concomitant non-drug treatments will be summarized in Table 14.1.5.3 entitled *Summary of Concomitant Non-drug Treatments* (Safety Population).

Corticosteroids that the subject takes or continues to take after the first dose of study medication will be summarized in Table 14.1.5.4 entitled *Summary of Corticosteroids* (Safety Population).

Nephrotoxic medications that the subject takes or continues to take after the first dose of study medication will be summarized in Table 14.1.5.5 entitled *Summary of Nephrotoxic Medications* (Safety Population).

A listing of prior and concomitant medications will be provided for all enrolled subjects. A flag will be included in the listing to distinguish concomitant versus prior medications. Listing 16.2.8.7 entitled *Prior and Concomitant Medications and Non-drug Treatments* supports the analysis presented in Tables 14.1.5.1 through 14.1.5.5. This listing will be sorted by subject number and medication start date. A flag will be added to the listings to identify corticosteroids and nephrotoxic medications summarized in the tables.

9. STUDY DRUG ACCOUNTABILITY

A summary of study drug administration will be presented in Table 14.1.6 entitled *Summary of Administration of Study Drug* (Safety Population). The total duration of treatment in days will be summarized with descriptive statistics: n, arithmetic mean, SD, median, range (*i.e.*, minimum and maximum values). Total Duration will be calculated as the last date of treatment minus the first date of treatment + 1 day. Treatment duration will also be presented using a series of non-overlapping categories. The number and percent of each treatment duration category will be presented using counts and percentages. The treatment duration categories will be presented using the following categories:

- 1 to 28 Days
- 29 to 112 Days
- 113 to 196 Days
- 197 to 280 Days
- 281 to 364 Days
- > 364 Days

Listing 16.2.5.1 entitled *Administration of Study Drug* will support the analysis presented in Table 14.1.6. This listing will be sorted by subject number and relative day.

Listing 16.2.5.2 entitled *Study Drug Accountability* presents the accountability of the study drug including the number of sachets dispensed, the number of used sachets returned, and the number of unused sachets returned. This listing will be sorted by subject number and date dispensed.

10. EFFICACY

Observed values and changes from baseline in timed function tests and NSAA total score will be summarized using descriptive statistics for the evaluable population.

10.1. Timed Function Test

The timed function tests will be performed on the first day of treatment (Visit 2 - Study Day 1), Week 28 (Visit 5 - Study Day 196), and Week 52 (Visit 7/ET - Study Day 365). Results summarizing the baseline values (Study Day 1), post-baseline values, and the change from baseline values will be presented separately for each of the 4 tests:

- Time taken to run/walk 10 meters,
- Time taken to climb four standard sized stairs,
- Time taken to descend four standard sized stairs, and
- Time to stand up from a supine position

If the time taken to perform a test exceeds 30 seconds or if a subject cannot perform the test due to disease progression, a value of 30 seconds will be set for the summary analysis. A sensitivity analysis will also be performed using a maximum time threshold of 45 seconds instead of 30 seconds.

The time values in seconds will be summarized using descriptive statistics: n, mean, SD, median, range, and 95% confidence intervals. Only paired quantitative data will be summarized in the tables; all data will be presented in the listings. Results will be summarized and presented in Table 14.2.1 entitled *Summary of Timed Function Tests by Visit* (Evaluable Population). The supportive listing will be Listing 16.2.6.1 entitled *Timed Function Tests*. This listing will be sorted by subject number and relative day.

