8. SCHEDULE OF EVENTS AND STUDY PARAMETERS

8.1. Schedule of Events

The types and timing of data to be recorded are summarized in Table 2. Please see [Section 8.2](#) for explanations of the study procedures outlined.

Table 2: Schedule of Events

	Screening	Ataluren Treatment						4-Week Follow-Up
Day (± 2)	-28	1 ^a	28	112	196	280	364	392
Weeks	-4	0	4	16	28	40	52/ET ^b	56
Visit	1	2	3	4	5	6	7	8
Informed consent	X							
Clinical and medication history	X							
Vital signs	X	X	X	X	X	X	X	X
Height	X	X	X	X	X	X	X	X
Weight	X	X	X	X	X	X	X	X
Physical examination	X	As clinically indicated						X
Hematology	X	X	X	X	X	X	X	X
Blood sample for gene sequencing ^c	X							
Biochemistry ^d	X	X	X	X	X	X	X	X
Urinalysis	X	X	X	X	X	X	X	X
12-lead ECG	X		X				X	X
Timed function tests		X			X		X	
North Star Ambulatory Assessment		X			X		X	
Blood for ataluren PK ^e		X	X					
Palatability questionnaire			X					
Drug administration		X-----X						
Adverse events		X-----X						X
Concomitant medications	X							X
Non-DMD-related adverse events								X

^a All study and laboratory assessments on the first day of treatment must be done prior to ataluren dosing.

^b Patients who terminate the study early should complete all assessments required for Week 52/ET (Visit 7) and will be required to return 4 weeks from the final dose of study medication for the 4-Week Follow-up Visit.

^c Verification that a blood sample has been drawn for sequencing of the dystrophin gene. A patient who has written documentation of a nonsense mutation as the cause of DMD need not wait for confirmatory results to start study drug as long as the confirmatory blood sample for gene sequencing was drawn.

^d Biochemistry laboratory assessments will include hepatic transaminases and additional parameters as specified in Section 8.2.7.2.

^e On Days 1 and 28, blood samples for PK assessment will be drawn pre-dose and 1 (± 15 min), 2 (± 15 min), 4 (± 30 min), 6 (± 30 min), 8 (± 30 min), and 10 (± 30 min) hours post-dose.

Abbreviations: ECG = electrocardiogram, ET = early termination, PK = pharmacokinetics

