8.2.1.3. End of Treatment

If the patient discontinues treatment prematurely, the procedures required for Week 52 (Visit 7/ET) should be performed before the patient leaves the study and the patient should return for the 4-Week Post-Treatment Follow-up Visit.

Please refer to [Section 10](#) for further details regarding patient withdrawal procedures.

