3.9. CINRG Natural History Population

The largest prospective multicenter study of the natural history of DMD, performed by the Cooperative International Neuromuscular Research Group (CINRG), enrolled more than 400

ambulant and non-ambulant male patients with DMD and collected a comprehensive set of clinical measures over a 10-year period. In order to illustrate the clinical benefit of ataluren in subjects ≥ 2 and ≤ 5 years of age in Protocol PTC124-GD-030-DMD, subjects from the CINRG database will be selected based on ≥ 2 and ≤ 5 of age-match at study entry. Additional selection criteria (i.e. baseline TFTs, NSAA scores, etc.) maybe selected if significant differences in baseline demographics are observed between the CINRG cohort and the Study 030 population. The data extracted from the CINRG database will include demographics at study entry, and available Timed Function Test and North Star Ambulatory Assessment by the same time points: study entry, Weeks 28 and 52. The selected CINRG data will be summarized similarly to Study 030.

The data extracted from the CINRG database will not be included in study databases with the data collected in PTC124-GD-030-DMD. That is, the CINRG data will not be included in the SDTM and ADaM databases which support the tables, listings, and figures for the study CSR and will not be included in the study submission package.

Instead, the data from the CINRG database will exist as standalone SAS datasets. Separate ADaM datasets, tables, and listings will be generated to present results from the natural history CINRG database alongside results from PTC124-GD-030-DMD. These summaries will be kept separate from the study CSR.

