10.2. North Star Ambulatory Assessment (NSAA)

NSAA will be performed prior to ataluren dosing on the first day of treatment (Visit 2), Week 28 (Visit 5), and Week 52 (Visit 7/ET). The NSAA consists of 17 activities. For each of the evaluations, the subject will be scored with a 0 (Unable to achieve independently), 1 (Modified method but achieves goal independent of physical assistance from another) or a 2 (Normal – no obvious modification of activity). The maximum score is 34; the sum of the responses to the 17 individual questions will be the total score. If fewer than 13 of the 17 activities are performed, the total score will be considered missing. If from 13 to 16 activities are performed, the total score will be calculated by multiplying the sum of the scores in the x activities that were performed by 17/x. If an activity cannot be performed due to disease progression/loss of ambulation, a score of zero will be assigned.

Recent updates to the NSAA have removed ‘Lifts Head’ from the total score. Although the results from all 17 items have been collected, a summary will be presented based on the 16 items without the result from ‘Lifts Head’. The results of these 16 items will be summed on an intra- subject basis to obtain the total score. The best total score is 32 and the worst is 0.

In addition, the logit score will be performed per a linear transformation of the NSAA score to a scale of 0 to 100 [Mayhew 2013] based on the following table. This table illustrates the transformation of the raw score to the linearized measurement on a scale of 0 to 100 via a logit transformation. For example, a male who scored 12 out of 32 on the NSAA (excluding his score on item12 – lifts head) can be calculated to have a linearized measurement of 42 out of 100.

Results from the 16-item NSAA subscale will be presented in Table 14.2.2.1 entitled *Summary of 16-item North Star Ambulatory Assessment Total Score by Visit* (Evaluable Population) and Table 14.2.2.2 entitled *Summary of 16-item North Star Ambulatory Assessment Logit Score by Visit* (Evaluable Population).

The results of the entire 17-item NSAA scale will be presented in Table 14.2.2.1.1 entitled *Summary of the North Star Ambulatory Assessment Total Score by Visit* (Evaluable Population).

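### TFT and NSAA values taken at early termination share the Week 52 label, so as the SAP is written they enter the Week 52 change from baseline whatever their timing

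*SAP*

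**What the plan says.** **Collection.** Footnote b of the protocol's schedule of events (Section 8.1, Table 2) reads: "Patients who terminate the study early should complete all assessments required for Week 52/ET (Visit 7"). Protocol 8.2.1.3 repeats this for premature discontinuation: "the procedures required for Week 52 (Visit 7/ET) should be performed before the patient leaves the study". In that schedule the Visit 7 assessments include both TFTs and NSAA. The only earlier ones are on Day 1 and at Week 28.

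**Analysis time points.** SAP 10.1 lists the TFT time points as Day 1, Week 28 and "Week 52 (Visit 7/ET - Study Day 365"). After baseline, SAP 10.2 lists "Week 28 (Visit 5), and Week 52 (Visit 7/ET") for the NSAA.

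**Tabulation.** The TFT table is titled "Summary of Timed Function Tests by Visit", and the NSAA tables are also by visit. For TFTs, "Only paired quantitative data will be summarized in the tables". The Evaluable Population in SAP 4 needs one dose and boys who "have baseline and at least 1 post-baseline measurement for TFTs, NSAA" or a palatability response. It sets no minimum follow-up.

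**External comparison.** SAP 3.9 extracts available CINRG TFT and NSAA data at "study entry, Weeks 28 and 52" and summarises them in the same way as Study 030, in outputs kept apart from the clinical study report.

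**The concern.** A row labelled Week 52 is read as change over 52 weeks of treatment. If a boy stops at Week 8, his tests are done under the Visit 7/ET label, and that label belongs to the Week 52 row. He would add about 8 weeks of change to a mean presented as a 52-week change. He would also be absent from the Week 28 row, so the two post-baseline rows would describe different sets of boys for a reason the table does not show.

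The row matters most in the CINRG comparison, which SAP 3.9 introduces to illustrate clinical benefit. Week 52 is the later of its two follow-up points. With a planned sample of 12, one or two misplaced values can be visible in a mean.

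The outcome also sits badly with two of the plan's own rules. SAP 5 says missing data are not imputed, yet a Week 8 value standing in the Week 52 row works much like an observation carried forward. Protocol 11.4 says patients who do not complete the planned observations are to be evaluated separately, yet the SAP's table list has no efficacy table that does so.

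**Working it through.** The plan states no figure to reproduce: the sample of 12 has no formal statistical basis (Protocol 11.1), and TFT and NSAA are summarised descriptively. The check is first a trace through the text, then an illustration of size.

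**Where an early-termination value can go**

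1. A boy stops at Week 8, about Day 56. The protocol has him do the Visit 7 TFTs and NSAA then.
2. He has a baseline and one post-baseline value, so he is in the Evaluable Population. His TFT values also meet the pairing rule.
3. The SAP offers two post-baseline visits, Week 28 (Visit 5) and Week 52 (Visit 7/ET). His record carries the second label.
4. Nothing redirects it. The SAP has no rule by actual day, no separate row and no sensitivity analysis without such values. The only tolerance is the ±2 days in the schedule header, which governs scheduling. The SAP's own schedule (Section 16) has no TFT or NSAA rows.

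The value therefore lands in the Week 52 row.

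**Size, as an illustration**

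Inputs: N = 12 (Protocol 11.1). The number of leavers k and the week t at which they are assessed are assumptions, because the documents give neither. Also assumed: change is linear in time, and leavers have the same slope as completers.

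Share of the 52-week mean change lost = (k/12) × (1 − t/52)

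| k | t (weeks) | Calculation | Lost |
|---|---|---|---|
| 1 | 4 | (1/12)(48/52) | 7.7% |
| 1 | 12 | (1/12)(40/52) | 6.4% |
| 1 | 26 | (1/12)(26/52) | 4.2% |
| 2 | 12 | (2/12)(40/52) | 12.8% |
| 3 | 4 | (3/12)(48/52) | 23.1% |

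With one leaver at Week 4, mean follow-up behind the row is (11 × 52 + 4)/12 = 48.0 weeks instead of 52.

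**Chance that it arises**

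P(at least one early leaver among 12) = 1 − (1 − d)^12. For assumed dropout d of 5%, 10%, 15% and 20% this is 46%, 72%, 86% and 93%. Protocol 11.1 mentions dropouts but gives no rate.

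**After the change**

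With Week 52 restricted to assessments near Day 364, no short follow-up enters the row and the lost share is 0. The Week 52 n falls from 12 to 12 − k when the k early-termination values lie outside the window.

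**The case against.** The strongest reply is that no sentence in the SAP says early-termination values are analysed as Week 52. The SAP 10.1 wording comes from a sentence about when tests are performed, and it ties the visit to Study Day 365, which a Week 8 value does not fit. SAP 3.3 also lists planned assessments by day, and SAP 5 rules out imputation. A careful programmer might keep such values out. That is fair as to intent, but it does not supply a rule: the shared label remains the only slot the value has, and the tables are built on that label.

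A reader might also infer more than the documents support:

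- **That the bias runs towards zero, or flatters the drug.** This needs linear change and equal slopes. A boy who leaves because he is declining could move the mean the other way. SAP 10.1 assigns 30 seconds to a TFT that cannot be performed because of disease progression, and SAP 10.2 assigns zero to such an NSAA activity. The documents give no rate of change for this age group.
- **That follow-up times are mixed on the Study 030 side only.** SAP 3.9 takes available CINRG data and gives no visit windows, so the spread of timing on that side is unknown.
- **That laboratory, vital-sign and ECG tables are equally affected.** The link there is weaker. The schedules share the 52/ET label and SAP 3.4.1 uses an equivalent one for ECG, but SAP 12.2 and 12.3 do not use it, and SAP 12.4 places the ECG at Day 364.

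It also stands that the consequence is limited. The endpoints are secondary, the primary analysis is of the 4-week period (Protocol 11.3), the TFT and NSAA listings are sorted by relative day, and treatment duration is tabulated in categories. The listings would show true timing, but they would not correct the table means or the comparison.

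**Conclusion.** The point holds for TFT and NSAA. Read together, the protocol's early-termination procedure and the SAP's combined visit label put a value from any time on study into the Week 52 change from baseline and into the Week 52 summary set beside CINRG. This goes beyond a missing detail, because the text as written produces a mislabelled result.

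Size and direction cannot be fixed from the documents. Under linear change and equal slopes, one leaver among 12 dilutes the Week 52 mean change by about 4% to 8% for departures between Week 26 and Week 4. Two leavers at Week 12 give about 13%. With no early leavers the effect is nil. No error rate is involved. The change is worth making because it is cheap and the Week 52 row feeds the external comparison, but the consequence is modest.

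**What to change.** 1. In SAP 10.1 and 10.2, define Week 52 by study day: a stated window around Day 364, with its width fixed before the data are summarised. In the same edit, reconcile Day 365 in SAP 10.1 with Day 364 in Protocol Table 2 and SAP 3.3 and 16.
2. Restrict the Week 52 row to in-window assessments. Show early-termination assessments outside the window in a separate early-termination row, with the study day of each.
3. Do not assign them to the nearest scheduled visit. With TFT and NSAA scheduled only on Days 1, 196 and 364, a Day 56 value is nearest to baseline (55 days away, against 140 to Day 196). If baseline is excluded it would go to Week 28 and mix follow-up times there.
4. Use the same early-termination row in other by-visit tables wherever the schedule shares the 52/ET label.
5. State in the table and in the CINRG comparison that Week 52 describes boys assessed in the window, with the n.

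The cost is a short visit-window table in the SAP and a Week 52 n lower by the number of out-of-window leavers. The real price is that Week 52 becomes a completers-only summary. If leavers differ from completers, that selection remains, so it should be stated openly and read alongside the early-termination row.
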